4.1. Study objectives

The primary objective is to evaluate the bioequivalence of the NEB/RAM 5/10 mg FDC (Test) versus NEB 5 mg + RAM 10 mg EC (Reference).

5. Investigational plan

5.1. Study configuration and structure

[figure not shown]
This will be an open label, randomized, two treatment, three period, three sequence, single dose partial replicate cross-over study to assess the bioequivalence of the Nebivolol/Ramipril 5/10 mg FDC (Test) versus Nebivolol 5 mg and Ramipril 10 mg administered as extemporaneous combination (Reference).

The study population will include 54 healthy males and females (18 subjects per each randomized sequence), aged 18 to 60 years inclusive, who successfully pass the Screening procedures and will receive single doses of Test and Reference formulations according to the assigned randomized sequence A, B or C, as described in the schematic study design in the section 5.2.

Subjects will undergo a Screening (to be performed within overall 4 weeks prior to 1st study PK session), three PK sessions with one single dose administration of the Test Formulation in one out of the 3 PK sessions and one single dose of the Reference Formulation in two of the 3 PK sessions as per sequence assigned by randomization. Each PK session is separated by a minimum of a 14-day period between each IMP intake. In each PK session, blood sampling for PK plasma assessment will be taken at predefined time points up to 72 hours (h) post-dose. An End of Study Visit will be performed 10-12 days after last treatment administration, resulting in an expected individual overall clinical study duration of about 10 weeks. In case of any serious adverse (drug) reaction (SAR), subject enrollment and treatment administration will be put on-hold or stopped. The study will be resumed only after the case has been discussed and a decision on how to proceed has been taken by the Sponsor.

Ramipril is reported to have an intra-subject variability above 30% for C_{max} and AUC in literature, thus falling in the definition of highly variable drug product (HVDP)⁽²⁾. In these cases, the EMA guideline on the investigation of Bioequivalence suggests to carry out a replicate study design (either a 4-period, full-replicate design or a 3-period, partial-replicate design) in order to evaluate the intra-subject variability of the reference formulation and use a scaled-average bioequivalence approach. Such design allows to widen the acceptance criteria for C_{max} to a maximum of 69.84 – 143.19% based upon the intra-subject variability of the reference formulation observed in the bioequivalence study. Details regarding the calculation of the widened acceptance limits can be found in section 12.3.3⁽³⁾.

5.2. Schematic study design

Treatment sequence A, B and C will be allocated to eligible subjects who will be randomized at the CROSS RESEARCH Phase 1 Unit.

A formal safety data review meeting with Sponsor's Team and the Principal Investigators (PI) is required only in case of severe or serious adverse events.

5.3.Study flow chart

Procedures	Screening	1 st + 2 nd + 3 rd PK sessions (sessions separated by a minimum 14-day wash-out period between dosing)																				End of Study visit	
		T+0 ¹ #	T+5'	T+15'	T+30'	T+45'	T+1h	T+1.25h	T+1.5h	T+2h	T+2.5h	T+3h	T+3.5h	T+4h	T+6h	T+8h	T+10h	T+12h	T+24h	T+48h	T+72h		10-12 days after last dose
Informed consent	X																						
Incl./Excl. criteria	X	X																					
Demography data	X																						
Medical history	X																						
Genotyping for CYP2D6	X																						
Physical examination	X ²	X																					X
Haematology, biochemistry, Urinalysis	X																						X
Pregnancy test (β-HCG) ⁹	X	X																					X
Serology (HIV, HBV, HCV)	X																						
Drugs of abuse ³ + alcohol test + cotinine urine test	X	X																					
Vital signs + 12-lead ECG ⁴	X	X							X							X			X	X			X
Check of study restrictions		X																					
Randomisation		X ⁵																					
Study Treatment Administration ⁶		X																					
Nebivolol and Ramiprilat PK sample collection ⁷		X	X	X	X	X	X	X	X	X	X	X	X	X	X	X	X	X	X	X	X	X	

Ramipril PK sample collection ⁷		X	X	X	X	X	X	X	X	X	X	X	X	X	X	X	X	X	X			
Prior and Concomitant medications	X		→																			
AE recording	X ⁸	X ⁸	→																			
Residence in Phase I unit ^{&}		→																				

¹ T+0 corresponds to time of Study Treatment Administration, all other assessments at this time point to be completed prior to dosing.

² At Screening, physical examination also includes body weight and height.

³ Drugs of abuse urine test cocaine and metabolites (COC 300), Amphetamine (AMP 500), Methamphetamine (MET 500), Marijuana (including Cannabinoids THC) (THC 50), Opiates (including Heroin Morphine and metabolites) (MOP 300), Methylenedioxymethamphetamine Ecstasy (MDMA 500), Methadone (MTD 300).

⁴ Vital signs include supine SBP and DBP, PR, RR, Frontal Body Temperature (°C). At Screening only, orthostatic BP is also included. Prior to dosing, Vital signs and ECG should be performed within 1 hour before dosing; Post-dose assessments are limited to SBP, DBP, PR and ECG to be performed within 30 minutes before the PK sampling.

⁵ Prior to dosing of the 1st PK session only.

⁶ One out of two study treatments as per randomized sequence.

⁷ A time window for blood sample collection is allowed as follows: ± 2 minutes for blood sampling from T+15' to T+4h; ± 5 minutes for blood sampling from T+5h to T+24h; ± 30 minutes for blood sampling at T+48h and T+72h.

⁸ At screening and pre-dose (for 1st PK session only), to record also any clinical event, not associated to a drug intake, prior to IMP administration that occurs for the first time or worsens after signing the informed consent

⁹ On serum at screening and on urine at each Admission to the clinical centre

* NOTE: Screening procedures shall start within 4 weeks prior to 1st PK study session (4 weeks also for genotyping). ALL screening procedures should be completed, and results made available prior to randomization/start of the first PK study session.

NOTE: T+0 study procedures might be completed the day prior to dosing, the exception being baseline vital signs, ECG and PK sampling that should be done immediately before dosing.

⁵ NOTE: re-Screening is allowed provided that the subject has not already been randomized.

[&] NOTE: Residence starts the evening before dosing and ends 72 h post dosing (each PK session). Subjects will be tested for SARS-CoV-2 infection by PCR/rapid antigen tests at screening and at each Admission to the Phase I Unit

5.4. Study Endpoints

5.4.1. Primary PK endpoints

Area Under the plasma concentration-time Curve (AUC) from time zero to the last quantifiable time point ($AUC_{(0-t)}$) and maximum plasma concentration (C_{max}) of NEB and RAM when administered as FDC film-coated tablet (Test) and as EC tablets (Reference formulation).

5.4.2. Secondary PK endpoints

- Relevant secondary standard pharmacokinetic parameters of NEB and RAM such as AUC from time zero to infinity ($AUC(0-\infty)$), AUC from time zero to 72h ($AUC(0-72)$) for NEB only, plasma terminal half-life ($t_{1/2}$), terminal elimination rate constant (λ_z), residual area (%AUCextrap), time to maximum plasma concentration (t_{max}), last quantifiable plasma drug concentration (Clast) and time corresponding to Clast (tlast) when NEB and RAM are administered as Test and Reference formulations.

5.4.3. Exploratory PK endpoints

- AUC from time zero to 72h ($AUC(0-72)$), t_{max} , λ_z , $t_{1/2}$, C_{max} , Clast and tlast of Ramiprilat when NEB and RAM are administered as Test and Reference formulations.

Other PK parameters for all the analytes can be derived if considered appropriate at the time of the analysis.

5.4.4. Safety endpoints

Incidence, intensity (severity), seriousness and treatment causality of Treatment Emergent Adverse Events (TEAEs, i.e. AEs that occur after the first study drug intake).

Changes in laboratory safety parameters, vital signs and 12-lead ECG will be compared versus baseline.

6. General specifications

6.1.Data validation

Medidata Rave EDC ® 2023.1.4 or subsequent version will be used as Electronic Data Capture system for data entry, by site personnel and for data cleaning and data locking by the Menarini Ricerche Data Management team. The eCRF data are elaborated to create the SDTM and ADaM CDISC standard datasets.

6.2.Computer system and software used

The software used for all summary statistics and statistical analyses will be SAS ® 9.04.01 or higher (SAS Institute, Inc.). All tables and listings will be produced using PROC REPORT or procedure specific output displays using output delivery system (ODS). The summary tables and listings will use SAS monospace font of size 6. The default page type will be A4 and the default page orientation will be landscape.

6.3.Coding systems

6.3.1. Clinical Terms

Concomitant diseases, medical procedures, and Adverse Events will be coded with MedDRA version 25.1 or subsequent.

6.3.2. Drugs

Drugs will be coded with WHO (ATC coding system) Drug version 202209 or subsequent.

6.3.3. Classification criteria

NA

6.4.Report type, language, format

The statistical output will be in word and .pdf format and in English language.

Dates will be presented with the DDMMMYYYY format.

Counts and percentages: xxx (xx.xx%)

Counts and percentages also including the count of the event of interest: xxx |xxx (xx.xx%)

Descriptive statistics:	N	xxx
	Mean	xxx.xx
	Median	xxx.xx
	SD	xxx.xxx
	Minimum	same precision as individual value
	Maximum	same precision as individual value
	Q1	xxx.xx (if present)
	Q3	xxx.xx (if present)

Character values will be left aligned.

6.5. Standard Operating Procedures (SOPs) to be followed

Code	Title
MR-GCS-DMST-201_SOP	Delegation of duties for Data Management and Biostatistics study activities
MR-GCS-DMST-208_SOP	Generation and Management of Randomization List
MR-GCS-DMST-210_SOP	Statistical Analysis Plan (SAP)
MR-GCS-DMST-210.1_WI	Sample Size Calculation

MR-GCS-DMST-211_SOP	Statistical Programs Writing
MR-GCS-DMST-211.1_WI	SDTM programming
MR-GCS-DMST-211.2_WI	ADaM programming
MR-GCS-DMST-211.3_WI	TLF programming
MR-GCS-DMST-212_SOP	SAS Use and Management

6.6.Data Transfer Agreements

Data not directly entered in eCRF are based on specific Data Transfer Agreements (DTA). In particular in the NEB-RAM-01 study the data that is not directly captured in the EDC system are the PK concentration results produced by the Analytical Laboratory Anapharm Europe, S.L.U..

For every activity performed by a laboratory, the relative procedures regarding collection, shipment and/or retention of samples will be detailed in the corresponding laboratory manual. The transfer of data to the Sponsor will be regulated with a dedicated Data Transfer Agreement (DTA).

Analytes concentrations will be provided according to the specifications defined in the data transfer agreement between the CRO and the sponsor. The transfer of the PK concentration results is performed as per “DATA TRANSFER AGREEMENT PK Samples Tracking and Concentrations NEB-RAM-01” version 1.0 dated 03 October 2023.

The transfer of PK analysis results between the Sponsor and CROSS Research S.A is conducted following the specifications reported in the “DATA TRANSFER AGREEMENT PK Analysis NEB-RAM-01” version 1.0 dated 16 October 2023.

Results of the CYP2D6 analysis will be provided according to the specifications defined in the data transfer agreement between the analytical laboratory and the site.

For the details regarding DTAs and the management of the received data, please refer to the Clinical Data Management Plan.

7. Definitions and general methodology

7.1. Data quality assurance

All tables, figures, and data listings generated by Menarini Ricerche will be independently checked for consistency, integrity and in accordance with internal standard procedures.

7.2. General considerations and key definitions

7.2.1. General considerations

Study day is defined as the number of days from the date of first dose of study drug to the event/visit date. For dates equal to or later than the first dose of study drug, study day is calculated as follows. If the event happens after the first dose, it will be:

Study Day = Event or Visit Date – First Dose Date + 1

Instead, if the event happens before the first dose, the formula that will be used will be:

Study Day = Event or Visit Date - First Dose Date

Consequently, the day immediately prior to the first dose date is assigned as Day -1. The study day of the first dose of study drug is assigned as Day 1.

7.2.2. Key definitions

Baseline values

The baseline value of an assessment is defined as the last value measured before any intake of the study drugs.

Adverse Events (AEs)

Any untoward medical occurrence in a subject or clinical trial subject administered a medicinal product and which does not necessarily have a causal relationship with this treatment.

An AE can therefore be any unfavourable and unintended sign (including an abnormal laboratory finding), symptom, or disease temporally associated with the use of a medicinal product, whether considered related to the medicinal product.

Treatment-Emergent Adverse Events (TEAEs)

A Treatment-Emergent Adverse Event (TEAE) stands for an AE that occurs for the first time or that worsens in terms of seriousness or severity after the first study drug intake.

Drug Relationship

The relationship between an AE and study drugs will be judged according to the following categories:

Certain: The AE occurs in a plausible time relation to the administration of the drug and cannot be explained by a concurrent disease or other drugs or chemicals. The response to withdrawal of the drug (dechallenge) should be clinically plausible. The event must be definitive pharmacologically or phenomenologically, using a satisfactory rechallenge procedure if necessary.

Probable: The AE occurs in a reasonable time relation to the administration of the drug, it is unlikely to be attributed to a concurrent disease or other drugs or chemicals and it follows a clinically reasonable response on withdrawal (dechallenge). Rechallenge information (AE reappearance after drug reintroduction) is not required to fulfil this definition.

Possible: The AE occurs with a reasonable time relation to the administration of the drug, but it could also be explained by a concurrent disease or other drugs or chemicals. Information on drug withdrawal (dechallenge) may be lacking or unclear.

Unassessable: The relationship cannot be judged because the information is insufficient or contradictory and cannot be supplemented or verified.

Unlikely: A causal relationship cannot be definitively ruled out, but other drugs, chemicals, or underlying disease provide plausible explanations and/or the temporal relation to the administration of the drug makes a causal relation improbable.

Not Related: Any of the following are present:

- existence of a clear alternative explanation, and/or;
- unreasonable temporal relationship between drug and event, and/or;
- non-plausibility.

Adverse Drug Reactions (ADRs)

An ADR is any untoward and unintended response to an Investigational Medicinal Product (IMP) related to any dose administered.

The definition implies a reasonable possibility of a causal relationship between the event and the IMP. This means that there are facts (evidence) or arguments to suggest a causal relationship.

An ADR is considered any AE for which the relationship is considered as:

1. Certain
2. Probable
3. Possible

4. Unassessable

An AE is not considered as ADR when the relationship is judged as:

5. Unlikely
6. Not related

Seriousness

An AE/ADR is considered serious when:

- results in death;
- is life-threatening;

NOTE: Life-threatening is considered any AE in which the subject was at risk of death at the time of the event; it does not refer to an event which hypothetically might have caused death if it were more severe.

- requires inpatient hospitalisation or prolongation of existing hospitalisation;
- results in persistent or significant disability/incapacity;
- is a congenital anomaly/birth defect;
- is another medically important condition that may jeopardise the subject or may require intervention to prevent one of the outcomes listed above. Any suspected transmission of an infectious agent via a medicinal product is considered serious and should be assessed under the category of medically important events in the absence of other seriousness criteria.

A Serious Adverse Event (SAE)/ Serious Adverse Reaction (SAR) is considered as serious when it fulfils at least one of the conditions for the definition of seriousness. An AE/ADR is considered as non-serious when it does not fulfil the conditions for the definition of seriousness.

Adverse Event (AE) / Adverse Drug Reaction (ADR) Intensity (Severity)

The intensity level of a serious or a non-serious AE or ADR is attributed according to the following definitions:

- Mild: does not interfere with routine activities; in case of laboratory tests when there is a mild abnormality.
- Moderate: interferes with the routine activities; in case of laboratory tests when there is a moderate abnormality.
- Severe: makes it impossible to perform routine activities; in case of laboratory tests when there is a significant abnormality.

Adverse Event (AE) / Adverse Drug Reaction (ADR) Expectedness

An AE/ADR is considered **unexpected** when the nature, severity, or outcome of the AE/ADR is not consistent with the information provided in the safety sections of the Investigator Brochure, which includes as the Reference Safety Information (RSI) the information of Summary of Product Characteristics (SmPC) of Nebivolol (Nebilet® 5 mg tablet) and Ramipril (Delix protect®, Cardace®, Triatec® or Tritace® 10 tablet).

The definition of ADR also covers medication errors and uses outside what is foreseen in the protocol, including overdose, misuse and abuse of the product.

Serious Unexpected Adverse Drug Reaction (SUSAR)

Any serious adverse event judged by the Investigator or the Sponsor as drug-related, i.e. Serious Adverse Reaction (SAR; see section 9.5.1.4) and unexpectedly qualifies as a Suspected Unexpected Serious Adverse Reaction (SUSAR). As a general rule for this clinical study, all SARs should be considered unexpected even if listed in the SmPCs of Nebivolol (Nebilet® 5 mg tablet) and/or Ramipril (Delix protect®, Cardace®, Triatec® or Tritace® 10 tablet). or even if a SAR of the same kind has already previously occurred during the clinical study.

Therefore, all SARs occurring in the clinical study NEB-RAM-01 will be processed in accordance with the applicable regulations for SUSARs. SUSARs are subject to expedited reporting, as specified in section 9.5.3.2, as having a “Reasonable Possibility” of relationship with the IMP.

In case of any SAR, subject enrolment and treatment administration will be put on-hold or stopped. The study will be resumed only after specific discussion and agreement with the IEC and the CA.

7.2.3. Definition of terms and generation/transformation of PK variables

Please refer to appendix A

7.2.4 Criteria for handling concentrations below LLOQ

Please refer to appendix A

7.2.5 Criteria for the calculation of λ_z and related parameters

Please refer to appendix A

7.2.6 Anomalous values and exclusion of data

Please refer to appendix A

7.3. Analysis populations

Safety population: All subjects receiving at least one administration of study treatment.

Pharmacokinetic (PK) population: All subjects who have evaluable and reliable concentration-time data for deriving the study primary PK parameters for both the Reference and Test formulations and who did not experience major protocol violations or events impacting the PK results.

7.4. On study and pre-study closure activities

7.4.1. Data monitoring

This study will be monitored in accordance with the ICH Guidelines for GCP.

Monitoring procedures require that 100% of data are source data verified, particularly focusing on informed consents, adherence to inclusion/exclusion criteria, drug accountability, documentation of SAEs and the proper recording of efficacy and safety measurements.

All monitoring activities will be described in detail in the study-specific monitoring plan.

7.4.2. Protocol Deviations and Data Review Meeting

Major or minor protocol deviations are defined as those deviations from the protocol likely to have an impact on the PK or safety of study treatments.

Before any analyses of the data, a data review meeting (DRM) will take place to identify protocol deviations and any other episode that could affect the evaluation and reliability of concentration-time data. Such cases will be discussed, and on a case-by-case basis it will be determined whether to exclude the patients from the PK population. The final decisions on which patients to include or exclude from the PK populations will be finalized prior to database lock.

The following categories of protocol violation will be investigated in the DRM in order to identify subjects experiencing major or minor protocol violations:

- Informed consent not given

- Violation of inclusion/exclusion criteria (present at study start and/or developed during the study)
- No withdrawal from the study despite development of withdrawal criteria
- Violation of visit schedule (outside the window of acceptability defined in the study protocol)
- Violation from treatment
- Concomitant medication discordant with study protocol
- Factors interfering with drug uptake (e.g., vomiting after oral drug intake)
- Further protocol deviations not mentioned.

The minor and major protocol violations will be discussed during the review meeting and reported in the data review meeting report.

After the pre-analysis evaluation has been done, the database will be locked.

8. Determination of sample size

A sample size of 42 subjects (14 subjects per each of the sequences A, B and C) is considered adequate for testing the bioequivalence between each of the two NEB/RAM 5/10 mg FDC (Test formulation) and NEB 5mg + RAM 10 mg EC (Reference formulation) at 5% (one side) level of significance with a power higher than 80% based upon a Test versus Reference ratio varying between 0.95 and 1.05 and an intra-subject coefficient of variation of a maximum of 36.2%. ^{(1), (2)}

If a subject prematurely terminates his/her study participation for any reason not completing the three study sessions, he/she will be replaced with a new subject who will be randomised to the same sequence as per the replaced subject. The reason for replacement is based on the primary objective of the protocol i.e., to demonstrate the bioequivalence of Test vs Reference and study design (cross-over).

To account for approximately 22% of potential dropouts during the clinical phase and exclusions from the PK population, twelve extra subjects will be included into the study and a total number of 54 subjects will be randomized.

9. Randomization Methodology

The study will be performed according to an open design with treatment sequence allocated to each subject according to a randomization list; no blinding technique will be used.

The Global Biostatistic Department of Menarini Group will be responsible for generating the randomization list. The list should be kept at site. As soon as the subject's eligibility to be randomized is confirmed, the subject will be assigned to the lowest randomization number available in the list.

Each randomized subject will be allocated to one of the three treatment sequences.

Treatment sequences A, B and C are shown in table below:

	Study Session		
	1	2	3
Nebivolol/Ramipril 5/10 mg dose			
Sequence A	5/10 mg FDC	5/10 mg Extemporaneous Combination	5/10 mg Extemporaneous Combination
Sequence B	5/10 mg Extemporaneous Combination	5/10 mg Extemporaneous Combination	5/10 mg FDC
Sequence C	5/10 mg Extemporaneous Combination	5/10 mg FDC	5/10 mg Extemporaneous Combination

10. Stopping Rules and Blinding

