12.3.3 Analysis of Primary PK variables

Due to the replicate design adopted for the study, a dedicated approach will be performed to understand whether Ramipril is to be considered an HVD (high variable drug).

First, natural log transformed $AUC_{(0-t)}$ and C_{max} will be analysed using an ANOVA model including sequence, period treatment as fixed effects and subject within sequence as random effect.

After the statistical model has provided the results, the schematic approach below will be followed for Ramipril C_{max} :

After calculating variance of Ramipril C_{max} within Reference Formulation s_{wR}^2 from ANOVA, the coefficient of variation within Reference Formulation CV_{wR} can be calculated with the below formula:

$$CV_{wR} \% = 100 * \sqrt{\exp s_{wR}^2 - 1}$$

If it is true that

$$CV_{wR} > 30\%$$

Then, as EMA's approach suggests, Ramipril will be considered highly variable. Then, s_{wR} will be estimated following this rule:

$$s_{wR} = \begin{cases} \sqrt{s_{wR}^2} & \text{if } 30.00\% < CV_{wR} \leq 50.00\% \\ \sqrt{\ln[0.50^2 + 1]} \approx 0.4724 & \text{if } CV_{wR} > 50\% \end{cases}$$

From the value of s_{wR} it is possible to calculate the limits of the acceptance confidence interval:

$$[L; U] = 100 \exp \{ \mp k * s_{wR} \}$$

where k is the regulatory constant set to $k = 0.760$.

Below it can be seen some examples of how limits of acceptance confidence interval change according to different values of CV_{wR} .

CV_{wR}	Lower Limit L	Upper Limit U
30%	80.00%	125.00%
35%	77.23%	129.48%
40%	74.62%	134.02%
45%	72.15%	138.59%
$\geq 50\%$	69.84%	143.19%

The possibility to widen the acceptance criteria explained above does not apply to the Ramipril $AUC_{(0-t)}$ where the acceptance range should remain at 80.00 – 125.00% regardless of variability.

As anticipated, natural log transformed C_{max} and $AUC_{(0-t)}$ of Nebivolol and Ramipril will be analysed using a mixed effect model including sequence, period and formulation as fixed effects and subject within sequence as random effect.

Estimates of the mean difference (Test formulation – Reference formulation) and corresponding 90% CIs will be obtained from the model for each analyte.

The mean differences and 90% CIs for the differences will be exponentiated to provide estimates of the ratio of geometric means (Test formulation/Reference formulation) and corresponding 90% CIs.

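### The 5% one-sided level is stated without exception, but the prespecified widening rule for ramipril Cmax does not hold it: that test's type I error peaks at about 7% when the true reference CV is near 30%

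*SAP*

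**What the plan says.** **Sizing (SAP 8; same substance in protocol 10.1 and the synopsis).** "A sample size of 42 subjects (14 subjects per each of the sequences A, B and C) is considered adequate" for testing "at 5% (one side) level of significance with a power higher than 80" per cent, given a "Test versus Reference ratio varying between 0.95 and 1.05" and an "intra-subject coefficient of variation of a maximum of 36.2" per cent. Neither document separates ramipril Cmax from the other three primary tests here.

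**Design (SAP 5.1).** A "two treatment, three period, three sequence, single dose partial replicate cross-over study", with sequences TRR, RRT and RTR.

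**Rule for ramipril Cmax (SAP 12.3.3).** The within-reference variance comes from a `PROC GLM` fit to this trial's Reference data only. If the resulting CV_wR is above 30%, then, as the EMA "approach suggests, Ramipril will be considered highly variable", and the limits become exp(±0.760·s_wR), capped at the value for a CV of 50% (69.84–143.19%). Otherwise they stay at 80.00–125.00%. The CI is coded with `ALPHA=0.10` in either case. When the limits are widened, the point estimate must also lie within 80.00–125.00%.

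**Adjustment.** SAP 11.1 marks multiplicity as not applicable. Neither document evaluates the error rate of the two-step rule.

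**The concern.** A 90% CI gives a one-sided 5% test when the limits are constants. For ramipril Cmax the limits are random: the same estimate decides whether to widen and by how much. When s_wR is overestimated, the limits lie further out than the true variability justifies. The SAP writes its hypotheses with L and U as if they were fixed.

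At stake is the consumer risk on one of four primary criteria. All four must pass, so a product that truly fails only on ramipril Cmax is stopped by this test or by chance failure on another. A reader of the sample-size section would take the risk to be 5%.

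**Working it through.** **1. The plan's own figure.** Inputs from SAP 8: N = 42, CV 36.2%, ratio 0.95, one-sided 5%, fixed limits 80–125%.

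- s_w = √ln(1 + 0.362²) = 0.351
- SE = s_w·√(1.5/N) = 0.351 × √(1.5/42) = 0.0663, on 2N − 3 = 81 df; t = 1.664
- Lower side: (ln 0.95 − ln 0.80)/SE − t = 0.1719/0.0663 − 1.664 ≈ 0.93
- Upper side: (ln 1.25 − ln 0.95)/SE − t = 0.2744/0.0663 − 1.664 ≈ 2.47
- Normal approximation: 0.823 + 0.993 − 1 ≈ 0.82. Exact integration gives 81.5% at ratio 0.95 and 82.4% at 1.05.

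Thirty-nine subjects give 78.6%, so 42 is the smallest balanced number above 80%. Then 42/0.78 = 53.8, hence 54. The sizing is reproduced, and it uses fixed limits.

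**2. How often the limits widen by chance.** The Reference-only model has 84 observations and 44 parameters (42 subject, 2 period), leaving 40 df. At a true CV of 30%, s_wR = √ln 1.09 = 0.2936 and exp(0.760 × 0.2936) = 1.25, so the true limits are 80–125%. Widening then occurs when χ² on 40 df exceeds 40, which has probability 0.47.

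**3. Type I error of the whole rule.** Subject-level simulation of SAP 12.3.3 used the threshold, k = 0.760, the cap, the point-estimate constraint, the CI on 81 df and s_wR on 40 df, with 200,000 or more trials per case. The true ratio sits on the true limit: 1.25 for CV up to 30%, exp(0.760·σ_wR) above. Assumptions not in the documents are log-normal, complete, balanced data and equal Test and Reference variances.

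| True CV_wR | Limits widened | Type I error, N = 42 |
|---|---|---|
| 25% | 4% | 5.0% |
| 28% | 25% | 5.8% |
| 29% | 36% | 6.4% |
| 30% | 47% | 7.2% |
| 32% | 68% | 6.2–6.3% |
| 36.2% | 92% | 5.7–5.8% |
| 40% | 98% | 5.6% |
| 45% | >99% | 4.9% |
| 50% | >99% | 3.4% |

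Separate runs agreed to about 0.1 point. With 54 subjects the value at 30% is 7.2–7.3%. With fixed limits it is 5.0%.

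**4. Unequal variances.** With Reference CV 30%, the error is 6.3% at Test CV 25%, 8.1% at 35% and 8.7% at 40%. Part of the rise at 35% is not due to widening; it comes from the pooled residual variance. With σ_T² = ln(1 + 0.35²) = 0.1156 and σ_R² = ln 1.09 = 0.0862, the contrast variance is proportional to 0.1156 + 0.0862/2 = 0.1587. The pooled model uses about 1.5 × ½ × (0.0862 + ⅔ × 0.1587) = 0.1440. The SE is therefore understated by a factor √(0.1440/0.1587) = 0.95, and a fixed-limit test would also exceed 5%, at just under 6%.

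**5. Level that restores 5% at CV 30%.** Applied whether or not the limits widen, one-sided 0.034 gives 5.05% and 0.033 gives 4.9% (N = 42). Applied only when they widen, 0.034 leaves 6.0% at a true CV of 30% and 5.5% at 29%. With Test CV 35%, the level used in both branches still gives about 5.7%.

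**6. Power for ramipril Cmax at CV 36.2%, ratio 0.95, N = 42.** About 93% as planned, about 90% with the adjusted level, about 81% with fixed limits.

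**The case against.** The strongest reply is that this is the regulatory rule the plan cites. Threshold, constant, cap, point-estimate constraint and restriction to Cmax are all fixed in advance, and nothing in the documents calls for a smaller alpha. That stands: there is no departure from the cited approach, and the planned decision rule need not change. But citing the source of a rule does not make its level 5%.

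It can also be said that the 5% in SAP 8 is a nominal figure for a fixed-limit sizing. As a sizing statement it is correct. But the sentence covers the whole bioequivalence test, and neither document says that one of the four tests behaves differently.

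The excess is also local. That stands too: it is negligible at 25%, gone by 45%, and under one point at the planning CV.

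Three stronger readings are tempting and not supported:

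- **The trial's overall false-positive rate is 7%.** All four criteria must pass, so this test's rate is only an upper bound when ramipril Cmax alone is truly outside its limits.
- **Ramipril is expected to lie at the peak.** The documents say only that its variability is reported above 30%. They give no ramipril value near 30% and do not say which analyte the 36.2% belongs to.
- **The error is about 17% at a CV of 36.2%.** That follows only if the null is held at a ratio of 1.25. The SAP's null for ramipril Cmax uses the calculated limits.

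**Conclusion.** The point holds in a limited form. Both documents state 5% without exception, and the ramipril Cmax rule does not deliver it. Under equal variances and complete, balanced, log-normal data, the level rises from about 5.8% at a true CV_wR of 28% to a peak of about 7.2% at 30%, then falls to about 5.8% at 36.2%. It is higher if Test is more variable than Reference, about 8% at Test CV 35% and Reference CV 30%. The sample size is sound, and the cap and point-estimate constraint are already in these figures. What is missing is disclosure of the actual level and a sensitivity result that shows whether the conclusion depends on it.

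**What to change.** **Wording, in SAP 8 and 12.3.3.** Confine the 5% statement to the three comparisons with fixed limits (AUC(0-t) of both drugs, nebivolol Cmax). State that for ramipril Cmax 5% is nominal, and that the actual level can reach about 7% when the true CV_wR is near 30%.

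**Reporting.** Keep the planned decision rule. In Table 1.2 of the pharmacokinetic tables (SAP 13.2.1), add two ramipril Cmax results, labelled as sensitivity analyses that do not govern the conclusion:

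1. The planned 90% CI against 80.00–125.00%.
2. The same two-step rule with a CI of about 93.4% (1 − 2 × 0.033), applied whether or not the limits are widened. Re-derive the level for the final number of evaluable subjects, and state that it holds 5% only if Test and Reference variances are equal.

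**Cost.** A slightly less favourable stated level, and one extra CI from the model already fitted. The primary analysis is unchanged, so the requirement in protocol 10.5 for a substantial amendment when that analysis changes is not triggered. It would be if the adjusted interval were made decisive; power for ramipril Cmax at CV 36.2% and ratio 0.95 would then be about 90% instead of 93%.
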